4.3. Exclusion Criteria

Subjects are excluded if they meet any of the following criteria:

1. Positive for presence of human immunodeficiency virus type 1 or 2 (HIV1 or HIV2), hepatitis B, hepatitis C, human T-lymphotrophic virus1 (HTLV1) or -2 (HTLV-2), active syphilis. Note that subjects who have been vaccinated against hepatitis B [hepatitis B surface antibody-positive] who are negative for other markers of prior hepatitis B infection [e.g., negative for hepatitis B core antibody] are eligible. Subjects with past exposure to HBV [HBc Ab positive and/or HBe Ab positive] are also eligible for the study provided they are negative for HBV DNA. Subjects who are positive for anti-hepatitis C antibody are eligible as long as they have an undetectable hepatitis C viral load. Where clinically and/or regionally indicated, other tests may be performed, in which case relevant positive results suggesting active infection would exclude the subject from participating, depending on regional guidelines: for example, malaria, tuberculosis, active toxoplasmosis, Trypanosoma cruzi, or West Nile Virus.
2. Clinically significant, active bacterial, viral, fungal, or parasitic infection, as determined by the Investigator, e.g., active relapsing malaria.
3. Inadequate bone marrow function, as defined by an ANC of $< 1 \times 10^9/L$ ($< 0.5 \times 10^9/L$ for subjects on HU treatment) or a platelet count $< 100 \times 10^9/L$
4. Previous Exclusion Criterion #4 is no longer applicable as of Protocol Amendment 8.0.
 - 4.1 Severe cerebral vasculopathy, defined by any history of: overt ischemic or hemorrhagic stroke, abnormal TCD (> 200 cm/sec) requiring chronic transfusion, occlusion or stenosis in the circle of Willis, or presence of Moyamoya disease. Subjects with radiologic evidence of silent infarction in the absence of any of the above criteria would still be eligible.
5. Previous Exclusion Criterion #5 is no longer applicable as of Protocol Amendment 8.0.

6. Previous Exclusion Criterion #6 is no longer applicable as of Protocol Amendment 8.0.
7. Previous Exclusion Criterion #7 is no longer applicable as of Protocol Amendment 8.0.
8. Baseline oxygen saturation < 90% without supplemental oxygen (excluding periods of SCD crisis, severe anemia or infection).
9. Baseline carbon monoxide diffusing capacity (DL_{CO}) < 50% (corrected for Hb) in the absence of infection. If DL_{CO} cannot be assessed due to age or cognition-related restrictions, there must be a normal respiratory exam, chest radiograph without pulmonary infiltrates, and oxygen saturation by pulse oximetry \geq 90% on room air.
10. Baseline left ventricular ejection fraction (LVEF) < 45% measured by cardiac echography.
11. Clinically significant pulmonary hypertension at baseline, as defined by the requirement for ongoing pharmacologic treatment or the consistent or intermittent use of supplemental home oxygen.
12. Baseline estimated glomerular filtration rate (eGFR) < 70 mL/min/1.73 m², as determined using the Chronic Kidney Disease Epidemiology Collaboration (CKD-EPI) equation (see http://www.kidney.org/professionals/kdoqi/gfr_calculator.cfm).
13. Advanced liver disease, defined as:
 - a. Persistent aspartate transaminase, alanine transaminase, or direct bilirubin value $> 3 \times$ the upper limit of normal (ULN), **or**
 - b. Baseline prothrombin time or partial thromboplastin time $> 1.5 \times$ ULN, suspected of arising from liver disease, **or**
 - c. Magnetic Resonance Imaging (MRI) of the liver demonstrating clear evidence of cirrhosis, **or**
 - d. MRI findings suggestive of active hepatitis, significant fibrosis, inconclusive evidence of cirrhosis, or liver iron concentration ≥ 15 mg/g require follow-up liver biopsy in subjects ≥ 18 years of age. In subjects < 18 years of age, these MRI findings are exclusionary, unless in the opinion of the Investigator, a liver biopsy could provide additional data to confirm eligibility and would be safe to perform. If a liver biopsy is performed based on MRI findings, any evidence of cirrhosis, bridging fibrosis, or significant active hepatitis will be exclusionary.
14. For subjects who have history of iron overload or serum ferritin levels > 1000 ng/mL, a cardiac MRI is required. Cardiac T2* < 10 ms results in exclusion.
15. Contraindication to anesthesia.
16. Any contraindications to the use of plerixafor during the mobilization of HSCs and any contraindications to the use of busulfan and any other medicinal products required during the myeloablative conditioning, including hypersensitivity to the active substances or to any of the excipients.
17. Any prior or current malignancy or immunodeficiency disorder, except previously treated, non-life threatening, cured tumors such as squamous cell carcinoma of the skin.
18. Prior receipt of an allogeneic transplant.

19. Immediate family member with a known or suspected Familial Cancer Syndrome (including but not limited to hereditary breast and ovarian cancer syndrome, hereditary non-polyposis colorectal cancer syndrome, and familial adenomatous polyposis).
20. Diagnosis of significant psychiatric disorder of the subject that, in the Investigator's judgment, could seriously impede the ability to participate in the study.
21. Pregnancy, or breastfeeding in a postpartum female, or absence of adequate contraception for fertile subjects. Females of childbearing potential must agree to use a medically acceptable method of birth control such as oral contraceptive, intrauterine device, barrier and spermicide, or contraceptive implant/injection from time of consent through at least 6 months after drug product infusion. Male subjects must agree to use effective contraception (including condoms) from Conditioning through at least 6 months after drug product infusion.
22. Participation in another clinical study with an investigational drug within 30 days of Screening.
23. Previous Exclusion Criterion #23 is no longer applicable as of Protocol Amendment 8.0.
24. Prior receipt of gene therapy.
25. Previous Exclusion Criterion #25 is no longer applicable as of Protocol Amendment 9.0.
26. An assessment by the Investigator that the subject or parents/caregivers (as required) will not be able to comply with the study procedures outlined in the study protocol.
27. Patients needing therapeutic anticoagulation treatment during the period of conditioning through platelet engraftment (patients on prophylactic doses of anticoagulants not excluded per this criteria).
28. Unable to receive RBC transfusion.
29. Any other condition that would render the subject ineligible for HSCT, as determined by the attending transplant physician.
30. Applicable to subjects < 18 years of age only: Availability of a willing, matched HLA-identical sibling hematopoietic cell donor.

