--	--

	
concentration ≥ 15 mg/g require follow-up liver biopsy in subjects ≥ 18 years of age. In subjects < 18 years of age, these MRI findings are exclusionary, unless in the opinion of the Investigator, a liver biopsy could provide additional data to confirm eligibility and would be safe to perform. If a liver biopsy is performed based on MRI findings, any evidence of cirrhosis, bridging fibrosis, or significant active hepatitis will be exclusionary.
 
14. For subjects who have history of iron overload or serum ferritin levels > 1000 ng/mL, a cardiac MRI is required. Cardiac T2* < 10 ms results in exclusion.15. Contraindication to anesthesia.16. Any contraindications to the use of plerixafor during the mobilization of hematopoietic stem cells and any contraindications to the use of busulfan and any other medicinal products required during the myeloablative conditioning, including hypersensitivity to the active substances or to any of the excipients.17. Any prior or current malignancy or immunodeficiency disorder, except previously treated, non-life threatening, cured tumors such as squamous cell carcinoma of the skin.18. Prior receipt of an allogeneic transplant.19. Immediate family member with a known or suspected Familial Cancer Syndrome (including but not limited to hereditary breast and ovarian cancer syndrome, hereditary non-polyposis colorectal cancer syndrome, and familial adenomatous polyposis).20. Diagnosis of significant psychiatric disorder of the subject that, in the Investigator's judgment, could seriously impede the ability to participate in the study.21. Pregnancy, or breastfeeding in a postpartum female, or absence of adequate contraception for fertile subjects. Females of childbearing potential must agree to use a medically acceptable method of birth control such as oral contraceptive, intrauterine device, barrier and spermicide, or contraceptive implant/injection from time of consent through at least 6 months after drug product infusion. Male subjects must agree to use effective contraception (including condoms) from Conditioning through at least 6 months after drug product infusion.22. Participation in another clinical study with an investigational drug within 30 days of Screening.23. Previous Exclusion Criterion #23 is no longer applicable as of Protocol Amendment 8.0.24. Prior receipt of gene therapy.25. Previous Exclusion Criterion #25 is no longer applicable as of Protocol Amendment 9.0.26. An assessment by the Investigator that the subject or parents/caregivers (as required) will not be able to comply with the study procedures outlined in the study protocol.

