6.2.31. Pregnancy and Contraception

Pregnancy is neither an AE nor an SAE, unless a complication relating to the pregnancy occurs (e.g., spontaneous abortion, which requires reporting as an SAE). However, all pregnancies occurring during this study (in subjects or female partners of male subjects) are to be reported in the same time frame as SAEs using the Pregnancy Form. Serious adverse events during the course of a pregnancy experienced by a subject or female partner of male subject are required to be immediately reported (i.e., within 24 hours) on the SAE report form.

The course of all* pregnancies, including perinatal and neonatal outcome, regardless of whether the subject has discontinued participation in the study, will be followed until outcome, including

follow-up of the health status of the newborn at 6 weeks of age and annually thereafter for 2 years.

*Exceptions include:

In cases where the MALE was the study subject, pregnancies resulting from sperm banking prior to receipt of drug product will not be followed.

In cases where the FEMALE was the study subject, pregnancies resulting from oocyte banking prior to receipt of drug product in which the pregnancy is carried to term by surrogacy will not be followed.

Busulfan has been shown in animal studies to be teratogenic (see package insert for additional details). The effects of administration of bb1111 on the pregnant female or the developing fetus are unknown.

Female subjects of child-bearing potential are required to use 1 method of highly effective contraception from Screening to at least 6 months after drug product infusion, and male subjects of child-bearing potential are required to use 1 method of highly effective contraception from Conditioning to at least 6 months after drug product infusion. Beyond 6 months after drug product infusion, subjects should discuss with their physician prior to resuming unprotected intercourse.

Acceptable forms of highly effective contraception for female participants of childbearing potential or for partners of male participants who are of childbearing potential include:

- Combined (estrogen and progestogen containing) oral, intravaginal, or transdermal hormonal contraception associated with inhibition of ovulation
- Oral, injectable, or implantable progestogen-only hormonal contraception associated with inhibition of ovulation
- Intrauterine device
- Intrauterine hormone-releasing system

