- Bilateral tubal ligation or bilateral tubal occlusion (performed at least 3 months prior to screening)
- Vasectomized partner (performed at least 3 months prior to screening)
- Sexual abstinence (no sexual intercourse)

Acceptable forms of highly effective contraception for male participants include:

- Sexual abstinence (no sexual intercourse)
- History of vasectomy (performed at least 3 months prior to screening)
- Condom with spermicide used together with highly effective female contraceptive methods if the female partner(s) is of childbearing potential (see above for list of acceptable female contraceptive methods)

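### Exclusion Criterion 21 names barrier plus spermicide as an acceptable female method, but Protocol 6.2.31 requires a highly effective method over the same period and lists no barrier method for females

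*Protocol*

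**What the plan says.** Exclusion Criterion 21 appears in the synopsis and again in Protocol 4.3 with the same content. For females it reads: "Females of childbearing potential must agree to use a medically acceptable method of birth control such as oral contraceptive". The examples in full are "such as oral contraceptive, intrauterine device, barrier and spermicide, or contraceptive implant/injection", so barrier with spermicide is among them. For males it reads: "Male subjects must agree to use effective contraception (including condoms) from Conditioning through at least 6 months after drug product infusion". The female obligation runs from consent to at least 6 months after infusion.

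Protocol 6.2.31 sets a differently worded standard. Females of child-bearing potential "are required to use 1 method of highly effective contraception from Screening to at least 6 months after drug product infusion". Males have the same standard from Conditioning to at least 6 months after infusion. The section then gives two lists. The female list, which also covers partners of male subjects, is introduced as "Acceptable forms of highly effective contraception for female participants of childbearing potential". It names hormonal methods (each tied to inhibition of ovulation), intrauterine devices and hormone-releasing systems, tubal procedures, a vasectomized partner and abstinence. The male list has abstinence, vasectomy and one barrier entry: "Condom with spermicide used together with highly effective female contraceptive methods if the female partner(s) is of childbearing potential".

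The same section states that busulfan is teratogenic in animal studies and that the effects of bb1111 on a pregnant female or fetus are not known.

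**The concern.** Two parts of one protocol tell sites what contraception is adequate, and they do not agree. The eligibility criterion does not refer to 6.2.31, and nothing in the protocol says which text governs. An investigator working from the criterion could reasonably tell a female candidate that barrier plus spermicide is enough, although 6.2.31 does not list it.

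The stake is subject safety around the conditioning agent, not inference. The schedules of events place serum pregnancy tests at Screening, before harvest and at preconditioning. The follow-up schedule (Table 4) lists none. For the 6 months after infusion, prevention therefore rests largely on the contraception instruction, which is a good reason for it to say one thing.

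**Working it through.** There is no figure to reproduce. The check is a comparison of each method named in Criterion 21 with the lists in 6.2.31.

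| Method named in Criterion 21 | Position in 6.2.31 | Result |
|---|---|---|
| Female: intrauterine device | Listed | Agrees |
| Female: oral contraceptive | Listed, if ovulation is inhibited | Agrees with a qualifier that Criterion 21 lacks |
| Female: implant or injection | Listed (progestogen-only), if ovulation is inhibited | Agrees with a qualifier that Criterion 21 lacks |
| Female: barrier and spermicide | Not listed | Conflicts |
| Male: effective contraception, condoms mentioned | Condom counts only with spermicide, and with a highly effective female method if the partner is of childbearing potential | Conflicts if Criterion 21 accepts condoms alone |

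Of the four female examples, one agrees outright, two agree subject to a qualifier, and one conflicts.

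**Period.** For females, Criterion 21 starts at consent and 6.2.31 at Screening. Section 4.4 requires consent before any Screening test, so the two starting points are effectively the same. For males both start at Conditioning. All obligations run to at least 6 months after infusion. No difference of study phase explains the difference of standard.

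**Wording of the standard.** Criterion 21 uses a medically acceptable method for females and effective contraception for males. Section 6.2.31 uses highly effective for both. The terms differ as well as the examples.

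**Could barrier plus spermicide still count as highly effective?** The lists are introduced as including certain methods and are not expressly exhaustive. But the male entry makes condom plus spermicide depend on a separate highly effective female method when the partner is of childbearing potential. That is hard to square with a barrier method alone meeting the standard.

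**The case against.** The strongest reply is that the two texts can be satisfied together. Criterion 21 gives examples and 6.2.31 is a mandatory requirement: "Female subjects of child-bearing potential are required to use 1 method of highly effective contraception". A subject with an intrauterine device, or with a listed hormonal method that inhibits ovulation, meets both. Anyone enrolled is still bound by 6.2.31, so its protection is not removed. Other safeguards exist too: pregnancy tests up to preconditioning, withdrawal for pregnancy before conditioning (section 4.5), and reporting of pregnancies, including those in partners, on the serious adverse event timeline. Exclusion Criterion 26 also lets the investigator exclude someone who will not be able to comply with study procedures.

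Much of this stands, and it limits the consequence. It does not remove the mismatch, because Criterion 21 names as acceptable a method that 6.2.31 does not list, and no text ranks the two.

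A reader might infer more than the documents support:

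- **That sites apply Criterion 21 at entry and 6.2.31 only later.** The periods coincide, and no hand-over is described.
- **That the whole Criterion 21 list is at odds with 6.2.31.** Only barrier plus spermicide is a clear female conflict. The missing ovulation qualifier is a lesser one.
- **That Criterion 21 declares condoms alone sufficient for males.** It can also be read as requiring that male contraception include condoms, which would fit the condom entry in 6.2.31.
- **That every subject using a barrier method is affected.** A male using a condom with spermicide together with a highly effective female method satisfies both texts.
- **That deviations could only be classified arbitrarily.** Section 6.2.31 is a stated requirement, and SAP 2.2 has deviation categories and major or minor status settled by review before database lock.

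**Conclusion.** The inconsistency is real but narrow. A female relying only on barrier plus spermicide can meet the eligibility criterion and not meet 6.2.31. A male relying only on condoms with a partner of childbearing potential is in the same position if Criterion 21 is read as accepting condoms alone.

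The conclusion rests on reading 6.2.31 as not counting barrier methods alone as highly effective. The male condom entry supports that reading, although the lists are not closed. The number of subjects in either position is not given and cannot be derived. Teratogenicity is stated from animal studies only. The point is a minor drafting inconsistency with a bearing on safety. It does not touch any endpoint, sample size, power figure or analysis, and it gives no ground for preferring one contraception standard over the other.

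**What to change.** Reconcile Exclusion Criterion 21, in both the synopsis and Protocol 4.3, with Protocol 6.2.31, so that one named standard and one list of acceptable methods apply at eligibility and on study. The reconciled text should settle three things: the status of barrier plus spermicide for females, whether the ovulation qualifier applies to hormonal methods at eligibility, and what the mention of condoms requires of males. Which standard and which methods apply is for the sponsor to decide.

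The cost is a wording change in three places, or a cross-reference once the standard is settled. The reconciliation needs no new procedure, visit or data item.

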4.4. Subject Screening and Registration

Subjects willing to participate in the study will provide written informed consent according to Good Clinical Practice (GCP). Written informed consent must be obtained before the conduct of any Screening tests.

Upon signing the informed consent, the subject will be registered and assigned a unique subject number. Once a subject number has been assigned, it cannot be reused. If the subject is re-enrolled after discontinuation, he/she will be assigned a new unique subject number.

4.5. Subject Withdrawal from the Study

Subjects have the right to withdraw from the study at any time for any reason. After giving informed consent and assent (as applicable), subjects may withdraw or be withdrawn from study

related procedures and treatments (e.g., apheresis, busulfan conditioning) under the following conditions:

- withdrawal of consent or assent
- the subject is unable to comply with protocol-defined visits or other requirements of the protocol
- pregnancy prior to conditioning
- adequate cells are not collected during harvests, or failure of transduced cells to be dispositioned for clinical use
- any medical condition which, in the opinion of the Investigators, would put the subject at risk for continuing treatment or follow-up studies

Although subjects have the right to withdraw from the study at any time, withdrawal after the start of conditioning and before administration of the drug product is strongly discouraged, as this would be considered deleterious to the subject. In such cases, it is likely that rescue will be required using the subject's stored unmanipulated HSCs (rather than transduced cells).

For subjects who withdraw consent or assent (if relevant), no further data will be collected on the subject; if they have received drug product, they are expected to enroll in the long-term follow-up study.

For subjects who withdraw for reasons other than withdrawal of consent, any SAEs open at the time of discontinuation should be followed up until resolution or are determined to be a stable or chronic condition. See also [Section 6.2.30.1](#) for AEs monitoring of subjects who withdraw from the study.

- If withdrawal is before drug product infusion, subjects should remain on study for at least 30 days after any invasive study procedure (e.g., mobilization, liver biopsy) before withdrawal. In the rare case a subject undergoes myeloablation and receives back-up cells instead of bb1111, subject should remain on the study for at least 3 months post myeloablation.
- If subject withdraws after drug product has been manufactured but before infusion, the drug product may be shipped to bluebird bio for additional process development and characterization studies.
- If withdrawal is after drug product infusion, subjects will be asked to complete the same assessments as specified in the Schedule of Events (SOE) for Month 24 (Early Termination Visit assessments) and are expected to enroll in the long-term follow-up study.

Subjects withdrawn from the study prior to drug product infusion may be replaced.

4.6. Screen Failures

Subjects are Screen Failures if:

- They sign the main informed consent form, but cannot finish assessments for Screening or are ineligible based on those assessments

Data collected on Screen Failure subjects will only include:

- Demography
- Eligibility criteria for which subject was ineligible or did not finish assessment
- Note: Serious adverse events (SAEs) must still be immediately reported for Screen Failure subjects from consent until the time they are determined to be a Screen Failure

Upon consultation with the Medical Monitor, screen-failed subjects may be allowed to re-screen to be assessed for eligibility to enter the study.

